## 2.1.1 General Definition

### 2.1.1.1 Study Day

The date of randomization is defined as **Day 1**.

A study day is defined as the number of days since the randomization and for a particular date it is calculated as follows:

Study day = Assessment date – randomization date + 1.

Day 1 is the reference point for separating pre- and post-randomization. For assessments performed before Day 1, the calculation is as follows:

Study day = Assessment date – randomization date.

### 2.1.1.2 Date of Last Dose

In general a study regimen stops if the combination is not given anymore, i.e. the date of last dose of study regimen is the earliest ‘date of last dose’ among the study drugs contained in the study regimen.

However, for the investigational regimen containing everolimus, the date of last dose of study regimen is the date of the last intake of the investigational drug everolimus. This is a conservative approach in that any events occurring while still taking everolimus will be considered on-treatment events, even if the complete regimen is no longer being administered.

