Control regimen	Drug regimen used post-randomization as a comparator to evaluate comparative effects of the investigational drug (i.e. the combination of MPA and a CNI- either tacrolimus or cyclosporine)		
Enrollment	Point/time of subject entry into the study; the point at which informed consent must be obtained (i.e. prior to starting any of the procedures described in the protocol)		
Extension	Study period from Month 12 visit to completion of Month 24 visit regardless of treatment status (i.e. can be on or off randomized regimen)		
Investigational regimen	The investigational drug regimen tested in the study post-randomization (i.e. the combination of everolimus and a CNI- either tacrolimus or cyclosporine)		
Lost to follow-up	Those subjects whose status is unclear because they fail to appear for study visits without stating an intention to withdraw and cannot be contacted		
Subject Number	A number assigned to each subject who enrolls into the study		
Period	A distinct stage in the subjects' participation in the study, each period serves a purpose in the study as a whole		
Premature subject withdrawal	Point when the subject exits from the study prior to the planned completi of all assessments, synonymous with study discontinuation, not the sam as treatment discontinuation		
Primary Treatment Period	Study period from randomization to completion of Month 12 visit, regardless of treatment status (i.e. can be on or off randomized regimen)		
Screening period	Period from signing informed consent to successful completion of the transplant procedure		
Study Completion	Point at which the subject came in for a final evaluation visit at Month 24 or complete discontinuation from the study if prior to Month 24		
Study drug/ treatment	Any single drug or drug regimen administered to the subject as part of the required study procedures in any study period, includes everolimus, tacrolimus, cyclosporine, basiliximab, MPA and corticosteroids		
Treated biopsy proved acute rejection (tBPAR)	An acute rejection episode documented by histological evidence for which anti-rejection therapy (e.g. steroids, antibody or increase in study regimen immunosuppression) was given.		
Treatment discontinuation	Point when subject permanently stops taking study/investigational or control treatment drug/regimen for any reason, not the same as study discontinuation/premature subject withdrawal		

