3.1 Study design

This is a 2-year, randomized, multicenter, open-label, 2-arm study evaluating graft function with everolimus and reduced CNI versus MPA and standard CNI in adult *de novo* renal transplant recipients (Figure 3-1). Consented subjects will enter the screening period and upon

Protocol No. CRAD001A2433

meeting eligibility criteria, including successful transplantation, will enter the initial 12 Month treatment period then continue in the next treatment period to Month 24.

Figure 3-1 Study design- Primary Treatment to M12, Extension to M24

Upon meeting eligibility criteria, approximately 2040 subjects (around 1020 per treatment arm) will be randomized (1:1) within 24 hr of transplantation, to the following treatment groups:

Group 1: Everolimus plus Reduced CNI (see Table 5-1 for CNI target trough levels)

Group 2: MPA plus Standard CNI (see Table 5-1 for CNI target trough levels)

Randomization will be stratified, within treatment groups, to balance; 1) recipients by donor type, living donors (LD), deceased standard criteria donors (SCD) and deceased expanded criteria donors ECD); 2) CNI usage, cyclosporine vs tacrolimus. The overall study population will contain no less than 50% recipients of living donor transplants and subjects taking cyclosporine will comprise no more than 20% of the population.

Subjects will commence the randomized study regimen within 24 hr post-reperfusion of the allograft and should continue on the assigned open-label study regimen until the Month 24 visit.

Induction therapy, with Basiliximab or rATG only, is mandatory for all subjects starting pre-or peri-operatively on the day of kidney transplant surgery (For details see Section 5.5.4). Corticosteroids are mandatory for all subjects through Month 24 and can be administered according to local practice but with a minimal daily dose of 5 mg prednisone, or equivalent. The study regimen/medication definition comprises either a) everolimus plus reduced CNI OR b) MPA plus standard CNI. Cyclosporine and tacrolimus dose adjustments will be made according to local trough values in order to maintain timely adherence to the protocol-specified ranges (See Table 5-1). Subjects are expected to remain on the original CNI (combined with everolimus or MPA) to which they were randomized until at least Month 24. However, if subjects discontinue either CNI due to AE/tolerability and can maintain everolimus or MPA

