combined with the alternate CNI, within respective target levels as per protocol, they will not be considered to have discontinued study regimen/medication.

The primary analysis of the trial is planned when the last subject has completed the Month 12 visit. All subjects are expected to continue to Month 24 on the randomized study regimen. If subjects discontinue study medication (i.e. everolimus plus reduced CNI or MPA plus standard CNI) prior to Month 24 they should remain in study to Month 24 on standard of care immunosuppression.

It is planned that subjects completing the study to Month 24 on treatment may consent to participate in a separate three year observational study to Month 60 to allow validation of the composite endpoint with graft and subject outcomes up to 60 months post-transplant.

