5.5.9 Discontinuation of study treatment and discontinuation from study

Discontinuation of study regimen

The Dosage administration records for everolimus, MPA, tacrolimus and cyclosporine will be used to record if a subject has permanently discontinued study treatment and why.

Possible reasons for study treatment discontinuation are:

- Adverse Event
- Lack of Efficacy
- Technical problems
- Subject/Guardian Decision
- Lost to follow-up
- Death
- Graft Loss

The investigator should discontinue a subject from their randomized treatment regimen if, on balance, he/she believes that continuation would be detrimental to the subject's well-being.

If, at any time throughout the study, the randomized treatment regimen or any component of the regimen is interrupted for longer than 21 consecutive days, unless being held due to an elective surgical procedure then study regimen should be discontinued.

Subjects who become pregnant while taking study medication must be discontinued from study medication and from the study, such pregnancies should be reported as SAEs to Novartis DSE and entered as AEs in the CRF, the reason for discontinuation of study medication should be recorded as AE and reason for discontinuation from study is pregnancy (see next section below).

Subjects who discontinue their randomized study regimen (any component whether everolimus, MPA or the CNI) should remain in the study, if possible, and receive standard of care immunosuppression, according to local practice, until completing the study at Month 24. Visits and assessments for such subjects are described in Table 6-1. All immunosuppressants after

discontinuation of study regimen must be recorded on the Concomitant Medication CRF under the Immunosuppressive category.

Subjects are expected to remain on the original CNI (combined with everolimus or MPA) to which they were randomized until at least Month 24. However, if subjects discontinue either CNI due to AE/tolerability and maintain everolimus or MPA combined with the alternate CNI, administered to respective target levels per protocol, they will not be considered to have discontinued study regimen/medication.

Discontinuation from Study and Study/Period completion

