### Switching CNIs

The number and percentage of patients of remaining on their initial CNI or switching CNI at least once during the study will be summarized for each study CNI-specific study regimen. This will be provided for each study period (up to Month 12, Month 12 to 24, and cumulatively).

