### 2.7.3.1 eGFR by CKD-EPI and Cystatin C-based Formulae

The renal function (eGFR by CKD-EPI and Cystatin C-based formulae) analyses will be based on on-treatment analysis without imputation. Renal function and change from Week 4 will be summarized by visit with descriptive statistics. A two-sided t-test will be performed to compare the two treatment groups at each visit. A plot of mean and 95% CI of eGFR by visit will be provided.

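### Read literally, the SAP's last-dose rule ends on-treatment time at a protocol-permitted CNI switch in the MPA arm but not in the everolimus arm

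*SAP*

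**What the plan says.** **Protocol.** Section 3.1 describes the regimen as "either a) everolimus plus reduced CNI OR b) MPA plus standard CNI", and the glossary describes the control regimen as "the combination of MPA and a CNI- either tacrolimus or cyclosporine". Both name the CNI as a class. Section 3.1 then covers a patient who gives up one CNI for an adverse event or poor tolerability and can keep everolimus or MPA "combined with the alternate CNI, within respective target levels as per protocol, they will not be considered to have discontinued study regimen/medication". Section 5.5.9 repeats the rule: "they will not be considered to have discontinued study regimen/medication". It applies to both arms. Stopping is recorded drug by drug: "The Dosage administration records for everolimus, MPA, tacrolimus and cyclosporine will be used to record if a subject has permanently discontinued study treatment".

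**SAP.** Section 2.1.1.2 gives the general rule: "In general a study regimen stops if the combination is not given anymore, i.e. the date of last dose of study regimen is the earliest" of the last-dose dates of the study drugs in the regimen. The next paragraph departs from it for the everolimus regimen, whose date is the last everolimus intake. The SAP calls this conservative, because events on everolimus still count after the full combination has ended.

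Sections 2.1 and 2.1.1.5 build the on-treatment windows on stopping study medication: 2 days in general, and 7 days for adverse events, infections and events of interest. Section 2.4.1 plans a table of patients "remaining on their initial CNI or switching CNI at least once during the study", so switching is foreseen. For CKD-EPI and cystatin C, section 2.7.3.1 says the "analyses will be based on on-treatment analysis without imputation".

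**The concern.** Tacrolimus and cyclosporine are separate study drugs with separate dosing records. An MPA patient who moves from tacrolimus to cyclosporine therefore has a last tacrolimus dose at the switch. If that is the earliest last dose in the regimen, on-treatment time ends there, although the protocol regards the regimen as continuing, possibly to Month 24. An everolimus patient with the same history stays on treatment until everolimus stops.

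The on-treatment definition would then differ by arm for identical conduct. It feeds these analyses:
- on-treatment non-serious adverse events, infections and events of interest
- laboratory and vital-sign tables
- the treatment-endpoint values of SAP 4.2.3
- duration of exposure
- the on-treatment efficacy and MDRD4 sensitivity analyses
- the CKD-EPI and cystatin C comparisons, which have no planned all-data version

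Patients who switch because of CNI intolerance are unlikely to be a random sample of the arm.

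**Working it through.** **1. The plan's own example.** SAP 4.2.3 takes a patient who stops study medication on Day 179, with systolic pressures of 155, 190 and 165 mmHg on Days 149, 180 and 189. With the 7-day rule the window closes on Day 179 + 7 = 186. The last value inside it is Day 180, so the Month 6 treatment endpoint is 190 mmHg, as the SAP states. A 2-day window (Day 181) gives the same value.

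**2. The same data with a CNI switch on Day 179, and MPA or everolimus continued.**

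| Rule | Regimen last dose | Month 6 treatment endpoint |
|---|---|---|
| MPA arm, earliest last dose read literally | Day 179 | 190 mmHg (Day 180) |
| MPA arm, the two CNIs treated as one component | after Day 189 | 165 mmHg (Day 189) |
| Everolimus arm, SAP rule | after Day 189 | 165 mmHg (Day 189) |

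The literal rule gives different answers by arm from identical data. Treating the CNI as one component removes the difference.

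**3. Time lost per MPA switcher to Day 360, 7-day window.** Days lost = 360 − (switch day + 7).
- Switch on Day 30: 323 days (90%)
- Switch on Day 90: 263 days (73%)
- Switch on Day 180: 173 days (48%)

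With the 2-day window the losses are 328, 268 and 178 days.

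**4. Time lost across the MPA arm to Month 24.** The switch share s is not in the documents; 2% to 15% is assumed, with the switch at Day 90. Month 24 is Day 720 (SAP Table 4-1). Share of on-regimen time lost = s × (720 − 90)/720 = 0.875 × s.
- s = 2%: 1.8%
- s = 5%: 4.4%
- s = 10%: 8.8%
- s = 15%: 13.1%

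The everolimus arm loses 0%. This is the exposure calculation. Crediting the 7-day window changes the factor to 623/720 = 0.865 and the range to 1.7% to 13.0%.

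**5. Effect on an adverse-event rate.** Assume an event with 20% incidence by Day 720 in both arms and constant hazard. Incidence by Day 90 is 1 − 0.8^(90/720) = 2.8%. The apparent MPA rate falls by s × (20 − 2.8) points: 0.9 at s = 5% and 1.7 at s = 10%. The standard error of the difference with 1,020 per arm is √(2 × 0.2 × 0.8/1020) = 1.8 points.

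A second set of assumptions gives the same direction. With 30% incidence by Day 360, a switch on Day 90 and the 7-day window, the apparent MPA rate is 29.6%, 29.0%, 27.9% and 26.9% for s = 2%, 5%, 10% and 15%.

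**6. On-treatment eGFR.** If switchers average d below the other MPA patients, leaving them out of later visits raises the MPA mean by s × d. The documents give neither s nor d. For an assumed d of 8 mL/min/1.73m², the shift is 0.16 at s = 2% and 0.8 at s = 10%.

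**The case against.** The best counter-argument is that the SAP sentence opens with the governing idea: a regimen stops when the combination is no longer given. The protocol's control combination is MPA plus either CNI, and after a switch that is still being given. SAP 2.1.1.5 ties on-treatment status to discontinuation of study medication, which by protocol 5.5.9 a qualifying switcher has not done. This reading is available and would reconcile the two documents. So a reader might infer a flat contradiction, but the text supports only an unresolved ambiguity. The operational half of the sentence still works drug by drug, as do SAP 2.3.1, which ranks tacrolimus and cyclosporine separately as sources of the discontinuation reason, and SAP 2.4.3.2, which lists four study drugs. A programmer could reasonably implement the literal rule.

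Second, the SAP's document history (10-Nov-2016) records that a definition of initial CNI stratum and CNI switch was added. No such definition appears in the text available, parts of which are redacted. It may bear on this point, so one can say only that no exception is visible.

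Third, the everolimus rule is declared conservative, and the likely distortions run against everolimus: fewer MPA events counted and, if switchers have poorer function, a higher MPA eGFR. That is fair, and no route to a false claim for everolimus is shown. But the stated rationale explains keeping everolimus events. It does not explain dropping MPA time that the protocol counts as on regimen.

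Fourth, the sizes depend on assumptions. If events cluster early, less is lost after Day 90 than constant hazard implies, and both adverse-event shifts illustrated against a standard error (0.9 and 1.7 points) are below one standard error (1.8).

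**Conclusion.** The point stands as a definition to be reconciled in the analysis plan. Taken literally, SAP 2.1.1.2 truncates MPA-arm switchers at the switch plus 2 or 7 days, against protocol 3.1 and 5.5.9, and does not truncate matching everolimus switchers.

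Two stronger readings are not supported. A reader might infer that MPA switchers vanish from every on-treatment analysis; in fact data before the switch are kept, and trough compliance (SAP 2.4.2.2) runs on each drug's own dates. A reader might also infer that harms in the MPA arm are undercounted generally; SAP 2.1 and 2.8.1 count SAEs and deaths whatever the treatment status. The primary, key secondary and main MDRD4 analyses use all available data and are untouched.

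The size is 1.8% to 13.1% of MPA on-regimen time to Month 24, against none for everolimus. It rests entirely on an assumed 2% to 15% switching at about Day 90. At the low end the effect is negligible. The comparisons most exposed are CKD-EPI and cystatin C eGFR, because no all-data analysis backs them up.

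**What to change.** State in SAP 2.1.1.2 that a CNI switch meeting the conditions of protocol 3.1 and 5.5.9 is not a regimen stop. For those patients, derive one CNI component date as the later of the last tacrolimus and last cyclosporine study doses. Then take the earlier of the MPA and CNI component dates as the MPA regimen's last dose. Use that date for exposure and for the 2-day and 7-day windows.

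The derivation must carry over the protocol's conditions (reason for the switch, and the alternate CNI at its target levels) and say how each is checked. A bare later-of-two-dates rule would not match the protocol. Protocol 5.5.5, which ends the regimen when either CNI is interrupted beyond 21 days, should be reconciled with 3.1 and 5.5.9 in the same note.

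The cost is one sentence and one derivation change on dosing records already collected. The downside is that switchers' later data enter the MPA on-treatment summaries, as they already do for everolimus. The arms would still differ for a CNI stopped without replacement. That difference follows from the SAP's stated everolimus rule, and a sensitivity analysis with one last-dose rule for both arms would show how much it matters.

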9.5.3 Safety variables

Safety variables to be assessed include discontinuation from study, discontinuation from treatment, AE/infection, SAE, notable events, laboratory tests, and vital signs. All safety analyses will be done on the safety set. Generally safety analyses will use treatment -emergent data (on-treatment analysis by including data up to 2 days after the discontinuation of study drug). Selected variables will be analyzed using all available data including data assessed beyond study treatment discontinuation: AEs/infections and deaths.

As subjects may not necessarily visit the clinics at the exact scheduled time, it may be misleading to lump all data with the same nominal visit number into the same visit in a by-visit analysis. Thus, all data are to be "re-aligned" by referencing their visit date to the date of initial dose. Visit-based time windows will be defined for data analysis.

The Baseline value is represented by the last observation during the Baseline period.

Amended Protocol Version v01 Clean

Assessment of premature study and study treatment discontinuation

Incidence rate of subjects who prematurely discontinue study medication or study will be summarized by frequency tables.

AEs/infections

Generally, infection data are analyzed together with AE data. In addition, infection data will be analyzed separately. Micro-organism will be additionally coded with NovORG dictionary.

The incidence of treatment-emergent AEs will be summarized by body system, severity and relationship to study drug. The type (viral, bacterial, fungal, and others) and micro-organism of infections will be tabulated. In addition, AEs/infections will be summarized per SMQ narrow search.

All information pertaining to AEs noted during the study will be listed by subject, detailing AE (verbatim given by the investigator as well as the preferred term according to the MedDRA dictionary), body system, date starting and ending, causality, severity and drug-relatedness.

Notable events

Notable events include death, non-fatal SAEs (including infections and rejections reported as SAE), AEs (including infections and rejections) leading to discontinuation from the study, and drop-outs due to notable events as reported on the Treatment/Study completion CRF): a) adverse event(s); b) abnormal laboratory result(s); c) abnormal test procedure result(s).

Vital signs

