### 2.8.1 AEs Including Infections

Generally, infection data are analyzed together with AE data. In addition, infection data will be analyzed separately. Micro-organism will be additionally coded with NovORG dictionary. AEs and infections here refer to treatment-emergent events (on-treatment analysis by including data up to 7 days after the discontinuation of study drug). Treatment-emergent adverse events are defined as adverse events or infections that started after the first dose of randomized study medication or events present prior to the first dose of randomized study medication but that increased in severity. Selected variables will be analyzed using all available data including data assessed beyond study treatment discontinuation: SAEs and deaths.

In all summaries about incidence rates of AEs/Infections, if a patient had multiple occurrences of an AE, the patient will be counted only once in the corresponding AE category. If a patient had multiple adverse events within a system organ class, he or she will be counted only once for that class. If a patient had multiple severity ratings for an AE, he or she will only be counted under the maximum rating.

The following AEs/infections will be analyzed by system organ class and preferred term:

- Any events (AEs/infections)
- Frequent events ( $\geq 10\%$  in any treatment group)
- Events requiring study drug dose adjustment or temporary interruption
- Events leading to premature discontinuation of study drug
- Events suspected to be study drug related
- Events requiring study drug dose adjustment or temporary interruption or leading to premature discontinuation of study drug
- Events by maximum severity
- Serious events (SAEs/serious infections)
- Serious events suspected to be study drug related
- Death

Subgroup analyses will be done for AEs and SAEs including infections for the following subgroups:

- CNI (tacrolimus vs. cyclosporine)
- Region: US, EU, Asia, Australia, Latin America, and Middle East

Summaries by standard MedDRA query (SMQ) level (level 1 to 4, SMQ - narrow search) and preferred term will be produced for AEs and SAEs including infections, with relative risks and their 95% confidence intervals displayed.

All information pertaining to AEs noted during the study will be listed by patient, detailing AE (verbatim given by the investigator as well as the preferred term according to the MedDRA dictionary), body system, date starting and ending, causality, severity and drug-relatedness.

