### 2.8.2 Safety Events of Interest

Safety events of interest, such as risks defined in the Safety Profiling Plan, Risk Management Plan or events of interest regarding signal detection or routine analysis are defined in the Program Case Retrieval Sheet (CRS) that is stored in CREDI at the path Cabinets/CREDI Projects/R/RAD001A/Integrated Medical Safety.

The following safety events of interest will be summarized with the number and percentage of patients experiencing the events, together with risk ratios (RRs) and 95% CIs. The version of the Case Retrieval Sheet used for the analyses will be described in a footnote. This includes MedDRA version and NMQ (Novartis MedDRA Queries) dictionary date.

- Anemia: Haematopoietic erythropenia (SMQ, broad search)

- Gastrointestinal ulcers: Gastrointestinal ulceration (SMQ, narrow search)  
This is a sub-SMQ under "Gastrointestinal perforation, ulceration, haemorrhage or obstruction (SMQ – narrow search)"
- Interstitial lung disease (CRS)
- Hyperlipidemia (CRS)
- Major cardiovascular events: Ischaemic heart disease and Cardiac failure (SMQ narrow search)
- Malignancy (CRS)
- NODM (See [Section 2.8.3.3](#))
- Peripheral edema (CRS)
- Proteinuria (associated chronic kidney disease) (CRS)
- Pleural effusion: MedDRA preferred term "Pleural effusion"
- Renal failure, excluding proteinuria (CRS)
- Stomatitis/mouth ulceration (CRS)
- Thrombocytopenia: Haematopoietic thrombocytopenia (SMQ, narrow search)
- Thrombotic and thromboembolic events: Embolic and thrombotic events (SMQ)
- Thrombotic microangiopathy (CRS)
- Wound healing events/disorders or complications: See [Section 4.4.1](#).

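### On-treatment time ends by a different rule in each arm; the effect is very small if the 21-day limit holds, but the SAP omits simple all-data checks for non-serious AEs and cystatin C eGFR

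*SAP*

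**What the plan says.** SAP 2.1.1.2 gives a default rule: "the date of last dose of study regimen is the earliest ‘date of last dose’ among the study drugs contained in the study regimen". This governs MPA plus standard CNI. For the everolimus regimen it makes an exception: "the date of last dose of study regimen is the date of the last intake of the investigational drug everolimus". The SAP calls the exception conservative, because events under everolimus still count when the full combination is no longer given.

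SAP 2.1 and 2.1.1.5 extend on-treatment time by two days for laboratory, vital-sign, efficacy and renal data, and by seven days for AEs and infections. SAP 2.8.1 defines the AE analysis accordingly ("on-treatment analysis by including data up to 7 days after the discontinuation of study drug"). SAP 2.8.2 and 2.8.3 compare the arms on selected events "together with risk ratios (RRs) and 95% CIs".

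On data after discontinuation, protocol 9.1 and 9.5.3 say: "Selected variables will be analyzed using all available data including data assessed beyond study treatment discontinuation: AEs/infections and deaths". SAP 2.8.1 says: "Selected variables will be analyzed using all available data including data assessed beyond study treatment discontinuation: SAEs and deaths".

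For renal function, SAP 2.1 makes all available data the primary basis and on-treatment data a sensitivity analysis, unless otherwise indicated. SAP 2.7.3.2 follows this for MDRD4, using the FAS with multiple imputation and then an on-treatment repeat. For CKD-EPI and cystatin C, SAP 2.7.3.1 instead states that "analyses will be based on on-treatment analysis without imputation".

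**The concern.** The two rules give different dates only when the CNI stops permanently before the partner drug. The everolimus patient then stays on-treatment until the last everolimus intake, while the MPA patient leaves at the CNI stop. With identical true event rates, the everolimus arm collects more counted events. The SAP's reason explains why events under everolimus should be captured. It does not explain why the comparator should have a shorter window when the two are divided into a risk ratio. Protocol 5.5.9 draws no such distinction when it describes regimen discontinuation: "Subjects who discontinue their randomized study regimen (any component whether everolimus, MPA or the CNI) should remain in the study".

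The rule reaches:
- on-treatment AE/infection incidences and risk ratios (SAP 2.8.1 to 2.8.3);
- the treatment-emergent SAE disclosure tables (2.8.5);
- on-treatment laboratory and vital-sign tables, and on-treatment efficacy and renal analyses (2.1, 2.7.3);
- exposure duration (2.4.1) and the definition of concomitant medication (2.4.3).

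An all-data analysis alongside would show whether the window matters. In the SAP's operative sections, neither non-serious AEs nor the cystatin C comparison has one. Cystatin C matters most here. CKD-EPI uses the same serum creatinine as MDRD4, which already has an all-data analysis, whereas the Hoek formula (SAP 4.5.2) is the only creatinine-independent measure.

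**Working it through.** The plan gives no figure to reproduce, so this is an illustration of size.

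**Inputs from the documents.** The lags are 7 days (AEs) and 2 days (other data). Protocol 5.5.5 and 5.5.9 end the regimen once a component has been interrupted for more than 21 consecutive days (5.5.9 excepts elective surgery). In SAP Table 4-1 the Month 9 window opens on Day 226 and the Month 12 window on Day 316. Months are 30 days.

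**Assumptions.** A share f = 2-20% in each arm stops the CNI first. The AE hazard is 0.03 per month and equal in both arms. Patients in the gap differ in eGFR from the others by d = -15 to +10 mL/min/1.73m². The documents give none of these.

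**AEs, CNI stop at Month 6.** Incidence = 1 - exp(-0.03 × months at risk).
- Full 12 months: 0.3023.
- MPA patient who stops: 6 + 7/30 = 6.233 months, 0.1706.
- Everolimus patient who stops, with the gap closed at 21 days: 6 + 28/30 = 6.933 months, 0.1878.
- Arm incidence = (1 - f) × 0.3023 + f × (incidence in those who stop).

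| f | MPA | Everolimus, 21-day limit | Risk ratio | Risk ratio, no limit |
|---|---|---|---|---|
| 2% | 0.2997 | 0.3000 | 1.001 | 1.009 |
| 20% | 0.2760 | 0.2794 | 1.012 | 1.095 |

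In the last column the everolimus arm's incidence is 0.3023, because everolimus runs to Month 12 without a CNI and still counts as study drug. Varying the hazard from 0.01 to 0.10 at f = 20% gives limited ratios of 1.013 to 1.011. CNI stops spread evenly over 360 days give 1.001-1.012 with the limit and 1.009-1.099 without.

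**eGFR, 21-day limit.** With a stop on Day 180, everolimus on-treatment time ends on Day 180 + 21 + 2 = 203. That is before both the Month 9 and Month 12 windows, so the shift there is zero. With stops spread evenly over 360 days and the visit on Day 360, the share of gap patients among those on treatment is:
- everolimus: f(23/360) / (1 - f + f × 23/360);
- MPA: f(2/360) / (1 - f + f × 2/360).

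The difference in shares is 0.0012 at f = 2% and 0.0143 at f = 20%. Multiplied by -15 and +10, the shift is -0.02 to +0.01 and -0.2 to +0.1. For scale, with SD 20 (protocol 1.1, tacrolimus minimisation study) and 816 per arm, the standard error of a mean difference is sqrt(2 × 400/816) = 0.99. Without the limit the shift is f × d, or -3.0 to +2.0 at f = 20%.

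**A separate issue.** An on-treatment-only eGFR comparison also selects patients after randomisation, and would do so under a common rule. The shift relative to all data is -(qE - qM) × d, where qE and qM are the shares off regimen in the everolimus and MPA arms and d is now the eGFR difference of off-regimen patients. If the shares differ by an assumed 0-10 points and off-regimen eGFR is an assumed 5-15 lower, the shift is 0 to 1.5 in favour of the arm with more discontinuation. This argues for the all-data eGFR analysis. It says nothing about the size of the last-dose artefact.

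**The case against.** The rule is disclosed and reasoned, and for AEs it works against everolimus, so conservative is a fair word for safety. After 21 days without a component the regimen is to be discontinued, and later immunosuppression goes on the Concomitant Medications CRF, not the dosing record. The long gaps behind the larger figures should therefore not arise. All of this stands and keeps the point minor.

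A reader might infer that no all-data check exists anywhere. The documents do not support that.
- Protocol 9.1 and 9.5.3 plan the AE/infection analysis, and SAP 2 keeps protocol section 9 in force unless otherwise indicated. The difficulty is that SAP 2.8.1 does indicate otherwise. The wording on SAEs, infections and death in SAP 2.1 may preserve all infections, but not other non-serious AEs.
- SAP 4.2.3 plans a study-endpoint summary of laboratory variables, including renal ones, from the last available value on or off treatment. It is descriptive LOCF, does not name cystatin C eGFR, and is not a comparison between arms.

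A reader might also infer that SAP 2.7.3.1 contradicts protocol 9.5.2, which bases renal analyses on the FAS. An analysis set is not a data window, and an on-treatment analysis can be run on FAS patients. The proper contrast is with the general rule in SAP 2.1.

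Finally, the concern about CNI switches is largely answered: protocol 3.1 and 5.5.9 say that a permitted switch is not a discontinuation. But the earliest-date rule in SAP 2.1.1.2 does not repeat this, and read literally it could end MPA-arm time at a switch.

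**Conclusion.** The point holds, as a minor one. The on-treatment window differs by arm, and no planned analysis applies one rule to both. If the 21-day limit is followed, the false AE risk ratio is about 1.001-1.013 and the Month 12 eGFR shift at most about 0.2 mL/min/1.73m². These sizes rest on the assumed 2-20% share, hazards and eGFR differences. The direction is against everolimus for AEs and undetermined for eGFR.

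A ratio near 1.10, or an eGFR shift of -3.0 to +2.0, should not be read into this. Both need the partner drug to continue for months as study drug without a CNI, which the protocol does not allow for. Nor does the point reach the primary and key secondary tests, the main MDRD4 analyses, or the all-data SAE and death summaries. The treatment-emergent SAE disclosure tables are within reach.

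Two omissions stand independently of the last-dose rule: the SAP narrows an AE/infection analysis that the protocol names, and cystatin C eGFR has no all-data comparison between arms.

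**What to change.** 1. In SAP 2.1.1.2, use one last-dose rule in both arms for on-treatment comparisons, for example last intake of everolimus or MPA. Use the any-component rule in both arms as a sensitivity analysis. Either rule, applied to both arms, removes the difference in how the window is defined.
2. State in the same section that a permitted CNI switch does not end the regimen, as in protocol 3.1 and 5.5.9.
3. Report by arm how many patients stopped the CNI first, and the days from that stop to the last intake of everolimus or MPA. This replaces the assumed share with a fact.
4. Restore in SAP 2.8.1 the all-available-data AE/infection summary named in protocol 9.1 and 9.5.3.
5. Repeat the cystatin C and CKD-EPI comparison of SAP 2.7.3.1 on all available FAS data from Month 6 onward. Protocol Table 6-1 (footnotes 7 and 10) schedules central laboratory tests, cystatin C included, for off-regimen patients from then. Earlier visits have no scheduled off-regimen samples.

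The cost is one re-derived date variable, some rerun tables, a short count by arm, and two added outputs (the AE/infection summary and the eGFR comparison). No new data are needed.
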